6. POTENTIAL RISKS AND BENEFITS

6.1 POTENTIAL RISKS

Risks Associated With LTLR-WB: The whole blood product to be utilized starting in the prehospital environment in the pilot clinical trial is the identical product to be used in the hospital and identical to the current whole blood product that has been transfused in over 200 patients over the last 24 months at the University of Pittsburgh without evidence of complications or transfusion reactions. The primary risk with LTLR-WB is a hemolytic transfusion reaction which will be followed as an important secondary outcome. There have been no hemolytic transfusion reactions in over 200 patients transfused LTLR-WB at the University of Pittsburgh in the last 24 months. The primary risks with any blood transfusion can be found in the Circular of Information prepared jointly by AABB, the American Red Cross, America's Blood Centers, and the Armed Services Blood Program. Those primary acute immunologic complications include hemolytic transfusion reactions, immune mediated platelet destruction, febrile nonhemolytic reactions, allergic reactions, anaphylactoid reactions and transfusion-related acute lung injury (TRALI). Delayed immunologic complications include delayed hemolytic reaction, alloimmunization, posttransfusion purpura, transfusion-associated graft-vs-host disease. Nonimmunologic complications include transmission of infectious agents, bacterial sepsis, transfusion-associated circulatory overload (TACO), hypothermia and metabolic complications.

The primary risk associated with transfusion of Rh+ blood into a woman of child-bearing potential (WCP) is hemolytic disease of the fetus and newborn (HDFN) of a future pregnancy. Complications of HDFN include fetal anemia, fetal hydrops, and in the most severe cases, fetal death. However, the overall risk of poor fetal outcome in a future pregnancy for Rh- women that are administered Rh+ blood products has been estimated to be less than 0.5%⁹⁰. Of note, the incidence of a female being Rh- is only 15%. This means that the majority of WCP are at no risk of Rh mismatch. For those WCP that are at risk, the likelihood of poor fetal outcome is very small.

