6.4.2 Data Safety Monitoring Plan

The proposed study will use the FDA definition of adverse events (AE) and serious adverse events (SAE). Any fatal or life threatening AE, which is unexpected and related or possibly related to study intervention, will be reported immediately to the IRB and may be followed by an additional letter detailing the nature of the SAE if needed. In the event that a participant either withdraws from the study or the investigators decide to discontinue a participant due to a SAE, the participant will be monitored by the co-PIs until (a) a resolution is reached (e.g., the problem has resolved or stabilized with no further change expected), (b) the SAE is determined to be clearly unrelated to the study intervention, or (c) the SAE results in death. Outcomes of related or possibly related SAEs will be regularly reported to the IRB, DSMB, and the sponsor. A summary of the SAEs that occurred during the previous year will be included in the annual progress report as well as in the annual IRB renewal.

Our DSMB responsibilities are listed as an appendix (Appendix 2). The DSMB will monitor accruing data in order to confirm patient safety throughout the trial. All study personnel will be trained on the protection of human subjects. Although the DSMB will make the final decision about the monitoring plan, we anticipate that the DSMB will evaluate the rate of adverse events between the treatment and control arms every 6 months during enrollment. The DSMB will also monitor primary, secondary study outcomes between the treatment and control groups including

main effects and a priori subgroups as specified elsewhere in the protocol. The DSMB will advise the investigators if a change in the protocol is warranted based on this monitoring.

The Medical Monitor is required to review all unexpected serious adverse events and other unanticipated problems involving risk to subjects or others. At a minimum, the medical monitor must comment on the outcomes of the event or problem and, in case of a serious adverse event, comment on the relationship to participation in the study. The Medical Monitor may review unblinded data in order to assist with his review.

Study Changes

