6.4.5 Reportable Adverse Events

Assessing and Reporting Adverse Events (AEs): Enrolled subjects will be monitored for adverse events throughout the first 48 hours after hospital admission. Reporting forms will be submitted to the DSMB and IRB. Potential adverse events occurring within the first 48 hours after admission will be reviewed as to treatment arm and further classified by: a) Severity (life-threatening, serious, non-serious); b) Expected vs. Unexpected; and c) Related, Possibly Related, Probably Not Related, or Definitely Not Related. For serious adverse events that are related or possibly related to the study or intervention, the coordinating center will notify the IRB and the DSMB as well as additional appropriate regulatory agencies and sponsor promptly. The coordinating center will tabulate and report compliance, data quality, and non-serious adverse events on a regular basis.

Expected adverse events are commonly observed in patients who are at risk of hemorrhage following traumatic injury and may or may not be attributable to the LTLR-WB. Clinical diagnoses of pneumonia, sepsis, cerebral bleeding, stroke, seizures, surgical interventions, complications due to specific injuries as well as other major medical or surgical complications are commonly

observed in these patients. They will be recorded as noted in the hospital discharge summary as complications and will not be reported as adverse events.

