Unanticipated Events Reporting: grade/severity, PI Assessment: Related/unrelated	Overall F(%)	Arm A Standard of Care F(%)	Arm B LTLR-WB F(%)	
1.				
2.				
3.				
4.				
5.				

Table 6: Protocol deviation

Protocol deviation	Overall F(%)	Arm A Standard of Care F(%)	Arm B LTLR-WB F(%)	
1.				
2.				
3.				
4.				
5.

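### Section 6.4.5 exempts listed complications from adverse-event reporting with no relatedness condition, against its own rule on related SAEs, and leaves several possible transfusion harms without a by-arm count

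*Combined protocol and SAP*

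**What the plan says.** Section 6.4.5 has two parts. The first sets adverse-event monitoring over the 48 hours after admission and classifies each event by severity, expectedness and relatedness. SAEs that are related or possibly related go promptly to the IRB and the DSMB.

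The second part deals with expected events. It names "Clinical diagnoses of pneumonia, sepsis, cerebral bleeding, stroke, seizures, surgical interventions, complications due to specific injuries as well as other major medical or surgical complications", says such events "may or may not be attributable to the LTLR-WB", and concludes: "They will be recorded as noted in the hospital discharge summary as complications and will not be reported as adverse events".

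Section 6.1 lists the risks of any blood transfusion. TRALI is among the acute immunologic ones, and for the rest: "Nonimmunologic complications include transmission of infectious agents, bacterial sepsis, transfusion-associated circulatory overload (TACO), hypothermia and metabolic complications".

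Section 6.4.2 anticipates that "the DSMB will evaluate the rate of adverse events between the treatment and control arms every 6 months during enrollment". It adds that the DSMB will monitor primary and secondary outcomes by arm. The 6.4.6 table has a column for SAEs that are expected and related. Only the DSMB receives these, at its next meeting.

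**The concern.** An exemption from adverse-event reporting for background trauma complications is a reasonable way to keep noise down. This one is defined by diagnosis alone. It applies to an event the product caused as much as to one the injury caused, and its last category has no limit. Staff who follow the closing sentence would file a sepsis from a contaminated unit as a discharge-summary complication. Staff who follow the opening paragraph would report the same event to the DSMB.

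At stake is the DSMB's view of harm in an open-label trial that enrolls under exception from informed consent (5.1), where Appendix 4 counts independent data monitoring among the protections owed to subjects.

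**Working it through.** The point rests on text, so the check sets the provisions side by side.

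**Step 1: follow one event.** Take a serious sepsis within 48 hours, expected in this population and possibly related to a transfused unit.

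- 6.4.5, first paragraph: prompt notice to the IRB and DSMB.
- 6.4.5, second paragraph: discharge-summary record only, not an adverse event.
- 6.4.6 table: DSMB at its next meeting; no requirement for the IRB, FDA or NHLBI; no reporting to the Medical Monitor.
- 6.4.2: outcomes of related or possibly related SAEs regularly reported to the IRB, DSMB and sponsor; Medical Monitor review is required for unexpected SAEs and unanticipated problems.

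These cannot all be followed. In the 6.4.6 table the DSMB is the only recipient of such an event, and the exemption can close that route.

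**Step 2: which exempt events are compared by arm another way?** Section 2.8 and Appendix 8 Table 4 were checked for each.

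- Pneumonia: yes, as nosocomial infection.
- Sepsis: in part, when it involves pneumonia or blood stream infection. Organ failure scores may reflect some of the rest.
- Stroke, cerebral bleeding, seizures: no row.

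Of the five named diagnoses, one is covered, one partly and three not at all (1 + 1 + 3 = 5).

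**Step 3: the transfusion risks in 6.1.** Acute hemolytic reactions have their own outcome. TRALI is seen only if it meets the Berlin ARDS definition. TACO has no row. Appendix 8 Table 5 is headed "Unanticipated Events Reporting: grade/severity" and includes a relatedness assessment by arm, but it covers unanticipated events, whereas 6.4.5 classes the listed complications as expected.

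**Step 4: what a count could show.** With 56 patients per arm, the chance of at least one event in an arm is 1 − (1 − p)^56. The values of p here are assumptions.

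- p = 5%: 1 − 0.95^56 = 0.94.
- p = 1%: 1 − 0.99^56 = 0.43.
- TRALI at the 1:12,000 quoted in 2.3: 0.005 if that rate is per patient. If it is per unit and all 56 receive the maximum 8 units (448 units), 1 − (1 − 1/12,000)^448 = 0.037.

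A by-arm count is useful for the commoner complications. For rare harms, the relatedness review of the single case is what matters. The exemption weakens both.

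**The case against.** The strongest reply is that the exemption should be read with the rest of the plan. The related-SAE rule opens the same section and makes no exception for the listed diagnoses, and 6.4.2 and 6.4.6 also route related SAEs to the DSMB. Background complications would then be exempt and product-related serious events would not. That may well be the intention, but the exemption does not say so, and it acknowledges possible attribution to the product immediately before excluding the events.

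Three stronger readings are tempting, and the documents do not support them.

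- A reader might infer that product harms escape the DSMB's arm comparison altogether. They do not: 6.4.2 has the DSMB monitor outcomes by arm, and these include mortality, organ failure, ARDS, pneumonia, blood stream infection and acute hemolytic reactions.
- A reader might infer that the six-monthly adverse-event rates would be nearly empty. Nothing in the documents gives that size. Related SAEs and non-serious adverse events are still to be reported.
- A reader might infer that TRALI and TACO are exempt outright. Neither is named; they fall under the exemption only if read into the open-ended class. The transfusion-reaction procedure in 6.4.6 lists circulatory overload and respiratory distress and calls for investigation. That procedure is headed prehospital, however, although up to 6 of the 8 units are given in hospital, and it reports to the medical record and Blood Bank with no by-arm report to the DSMB.

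It is also fair that Appendix 8 is a set of summary tables and not a specification of the DSMB report, that the DSMB may set its own monitoring plan (6.4.2, Appendix 2), and that its chair receives regular AE/SAE reports (6.4.3). This leaves room for the gap to be closed, but no text closes it.

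**Conclusion.** The concern holds in a limited form. Section 6.4.5 contains a rule that conflicts with its own first paragraph and with the 6.4.6 table for expected, related serious events, and sepsis caused by a transfused unit is the clearest case. Separately, stroke, cerebral bleeding, seizures, TACO, sepsis without pneumonia or blood stream infection, and TRALI not meeting ARDS have no by-arm tabulation, so the 6.4.2 comparison is incomplete for them. Unless someone judges such an event serious and related, with the arm known, no text puts it before the DSMB by arm.

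The number of events affected cannot be estimated from the documents. Two limits apply. The effect on adverse-event rates concerns the 48-hour window, since later events fall outside adverse-event monitoring in any case. And the conclusion on TACO and TRALI assumes that the open-ended class may be read to include them.

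**What to change.** Reconcile 6.4.5 with its own first paragraph and with 6.4.6. State that the exemption does not apply to events judged related or possibly related to a transfused product, or to transfusion complications named in 6.1 (including bacterial sepsis, TRALI and TACO), in either arm. State also which recipients and timing apply to expected, related SAEs, since the first paragraph and the table differ on this.

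Add one table to Appendix 8, by arm, giving the complications listed in 6.4.5 and the transfusion complications named in 6.1, and supply it at each DSMB meeting. The table should state its time window.

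The cost is protocol wording, a relatedness field and one table. The listed complications are already taken from discharge summaries. The documents do not show that TRALI and TACO are captured there, so those rows may need transfusion-reaction reports as a source. The relatedness judgment would be made open-label and is open to bias; the by-arm count does not depend on it, which is why both parts are needed.

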6.4.6 Adverse Events Reporting Timeline

Organization	Fatal/Life Threatening SUSAR	Non-fatal, non-life threatening SUSAR	SAE (expected and related)	UP (not involving risk)	UPIRTSO
IRB	24 hours	10 working days	No requirement	No reporting**	10 working days
FDA	7 calendar days	15 calendar days	No requirement	No requirement	14 days*
NHLBI	7 calendar days	7 calendar days	No requirement	No requirement	14 days*
Medical Monitor	24 hours	7 calendar days	No reporting	No reporting	14 days*
DSMB	24 hours	7 calendar days	At next meeting (every 6 months)	At next meeting (every 6 months)	14 days*

A table summarizing reporting timelines is provided below:

*Reporting occurs only after an IRB determination of UPIRTSO has been received

**No direct reporting is required; events are documented on a log that can be reviewed upon request

Prehospital Transfusion Adverse Events/Look Back Standard Operating Procedure (SOP):

a. Transfusion rate will be compatible with the patient's condition. The patient will be monitored closely during the entire transfusion. The documented start and stop times are directly related to the actual transfusion of the component. Study coordinators will assume responsibility of additional vital signs and completion of the whole blood

b. The patient medical record shall include the following:

- 1. Name of the components transfused
- 2. Donation identification number
- **3.** Date and time of transfusion (Start and Stop time)
- 4. Pre and post transfusion vital signs
- **5.** The volume or **#** of units transfused
- 6. The transfusionist's name (paramedic)
- 7. Documentation of related adverse events

c. Procedure for transfusion reactions:

This is modified from UPMC policy for Blood Transfusions to be applicable for this study.

1. Careful observation throughout the transfusion allows for early detection of adverse reactions and optimal treatment, if necessary. All reactions should be handled initially as possible hemolytic reactions and the transfusion must be stopped. Any adverse events associated with the transfusion of blood or blood components should be documented in the patient's Medical Record and reported to the blood bank/ transfusion service. Prehospital providers initiating transfusion of blood products will monitor vitals

throughout transport. If clinical concern for a transfusion reaction occurs, the transfusion will be stopped, and supportive care will continue. The concern for a transfusion reaction will then be communicated to the trauma center staff.

2. The most common clinical events accompanying or announcing transfusion reactions are, in order of decreasing frequency:

a. Fever, with or without chills

b. Skin symptoms, hives and/or itching or rash

c. Chest pain

d. Hypotension

e. Nausea

f. Flushing

g. Respiratory Distress (wheezing, coughing or dyspnea)

h. Bleeding at infusion site

i. Hemoglobinuria

j. Circulatory overload

k. Anaphylaxis

3. If an adverse reaction is suspected, the procedure below will be followed:

a. Stop the transfusion

b. Maintain IV access with Normal Saline and change the tubing.

c. Notify the patient's physician upon arrival to the ED and initiate immediate treatment as ordered.

4. For all other blood products involved in a reaction, all blood products shall be stopped and a transfusion reaction investigation shall be initiated per standard blood bank guidelines

5. Notify the Blood Bank of the suspected transfusion reaction.

6. Collect a sample drawn from the patient as soon after the reaction was detected. Send a 6 mls pink top tube, labeled with a new Blood Bank armband to the Blood Bank along with the unused blood, blood bag with attached hard back copy of the transfusion tag, the IV tubing used and the top 2 copies of the Transfusion Reaction Investigation 3 part form. The back copy of the Transfusion Reaction Investigation form should remain in the patient's chart as the initial report. A post transfusion reaction Urinalysis with Microscopic may also be ordered by the patient's physician.

7. The Blood Bank will complete the Transfusion Reaction initial report and notify the caregiver of the critical results. Pathology will evaluate the patient's reactions, Blood Bank's initial report, culture when indicated, and report will be documented in the patient's medical record. Consultation between the Medical Director of the Transfusion Service, the patient's physician and Risk Management is required when a fatal hemolytic transfusion reaction occurs. Further evaluation and FDA notification may be indicated. The participating centers Transfusion Service is responsible for peer review and blood utilization practice.

8. Look back procedures: Since the plasma will be tracked through the participating centers Blood Bank/Transfusion service look back/product recall procedures will be conducted as per standard protocol (**Appendix 6**).

6.4.7 Withdrawal of Subjects and Stopping Criteria:

Assuming a baseline in-hospital mortality risk of 33% in the control arm as was demonstrated in the recently completed PAMPer trial (manuscript in preparation) with all cause in-hospital mortality as the primary outcome, enrolling 56 patients in each arm, 112 total patients and using a 2 sided alpha of 0.05, the study will have a 80% power to detect a 22% (33% to 11%) or greater difference in in-hospital mortality. Based upon current PAMPer clinical

outcome data and the additional benefit attributable to LTLR-WB when it is initiated in the prehospital setting, the current proposed mortality difference is clinically meaningful and of sufficient magnitude to influence clinical practice for a pilot trial. The above sample size will provide more than sufficient power for the originally planned feasibility outcomes as we have increased our sample size by 24%. The above power analysis was generated assuming 2 sequential test are made using the O'Brien-Fleming spending function to determine test boundaries which are depicted in the following table and graph.

Details	Details when Spending = O'Brien-Fleming, N1 = 56, N2 =56, P1 = 0.1100, P2 = 0.3300							
		Lower	Upper	Nominal	Inc	Total	Inc	Total
Look	Time	Bndry	Bndry	Alpha	Alpha	Alpha	Power	Power
1	0.50	-2.96259	2.96259	0.003051	0.003051	0.003051	0.164669	0.164669
2	1.00	-1.96857	1.96857	0.049002	0.046949	0.050000	0.636252	0.800921
Drift 2.	.81024							

Discontinuation of the Clinical Trial:

The investigator may withdraw a subject from participating in this research if circumstances arise which warrant doing so. The decision may be made either to protect the subject's health and safety, or because the subject's condition did not meet certain criteria needed for study inclusion.

6.5 **RISKS MANAGEMENT PROCEDURES**

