2. RESEARCH DESIGN AND METHODS

2.1 CLASSIFICATION AND METHODOLOGICAL DESIGNS

The pilot study will be a 3 year, pragmatic, prospective, randomized, open label, clinical trial utilizing a busy level 1 trauma center with one of the busiest air medical services in the country where affiliations with local blood bank colleagues exist to provide cold storage LTLR-WB for the

prehospital (up to 2 units) and in-hospital setting (up to 6 additional units), up to 8 units total. There are 14 helicopter bases which fly patients to Presbyterian Hospital at the University of Pittsburgh. Some of the busiest air medical bases in the system will be utilized for the pilot trial. The pilot trial may need fewer or more bases added as enrollment proceeds. The study is required to be open label due to the inability to blind blood or blood component transfusion.

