2.6 RANDOMIZATION

Procedures Assuring Adherence to Randomized Assignment: Enrollment will occur in the prehospital phase of the trial and LTLR-WB or prehospital standard of care will be provided based upon randomization assignment. Prehospital providers will designate the patient as enrolled and notify receiving staff of the treatment arm. Research staff will be present upon arrival and will communicate directly with blood banking staff/anesthesia and the trauma team regarding the randomization arm of the patient. Once in-hospital, LTLR-WB randomized patients may receive LTLR-WB transfusion as indicated during this acute resuscitation phase of in-hospital care up to 6 units in-hospital and 8 units of LTLR-WB total.

Randomization and Blinding: A single stage cluster randomization scheme will be utilized. Designated air medical bases at the University of Pittsburgh will be block randomized and assigned to the LTLR-WB arm or Standard of Care (control) arm for 1 month time intervals. The cluster design will be at the level of the helicopter base. The block scheme will vary randomly between 2 and 4 month block sizes over the period of enrollment for the trial. Randomization assignments will be determined prior to the start of the bases enrollment following the above single stage cluster design using standard computerized randomization software. Communication with the blood bank transportation services and each respective air base will occur and an annual schedule of randomization assignment will be distributed to each study air base. This specific randomization scheme is required due to the limited supply of O+ LTLR-WB and also due to the logistics and delivery of the intervention in the prehospital setting. The

proposed pilot trial will be an open label trial as blood product transfusion requires appropriate documentation and essential look back procedures.

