2.9 STATISTICAL ANALYSIS

The overarching goals for the pilot trial are to evaluate safety, efficacy and feasibility of a LTLR-WB prehospital through in-hospital protocol to plan for the successful execution of a large, multicenter clinical trial. All analyses will be performed based on the intent-to-treat principle for the prehospital randomization and analyses will include all enrolled patients grouped by randomization assignment. This pilot study will guide the calculation needed for the large, multicenter clinical trial and will provide estimation for intra-cluster correlation coefficient and sample size variation across clusters. We will report 95% confidence intervals for all measurements

Safety and Efficacy Analysis: 28-day mortality is the primary safety and efficacy outcome and will be compared across randomized groups. Utilizing intention to treat principles we will compare the LTLR-WB and Standard of Care arms using a pooled Z test for comparing two independent proportions. We will additionally perform survival analysis for all mortality outcomes including 3hr, 6hr, 24hr, and 28day time points across the two arms of the study testing the differences using log rank test.

Eligibility, Enrollment, and Subject Accrual Anlaysis: The feasibility of enrollment will be evaluated by determining 1) the number of patients that meet the eligibility criteria for the trial; 2) the proportion of eligible patients that can be randomized and 3) the proportion of eligible patients who are enrolled in the trial. These proportions will be estimated directly as the observed ratio of numbers of patients, and 95% confidence intervals will be calculated to understand the likely range of values for a larger study with a comparable research protocol. The reasons why patients are not enrolled including frequencies of individual exclusions and the proportion of patients declining participation or not able to be randomized will be described. Rate of subjects' accrual per month with 95% C.I. will be calculated.

Adherence and Minimization of Bias: Adherence rates for each treatment arm of the protocol will be ascertained as the proportion of enrolled patients who adhere to the intervention (LTLR-WB vs. standard care) as assigned. Estimated proportions and 95% confidence intervals will be created. The trial has been designed to negate intervention arm crossover and maximize follow-up completion.

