3.3 EXCLUSION CRITERIA

- 1. Documented age: Age ≥90 or <18 years of age
- 2. Inability to obtain intravenous or interosseous access
- 3. Isolated fall from standing injury mechanism
- 4. Known prisoner or known pregnancy
- 5. Traumatic arrest with > 5 minutes of CPR without return of vital signs
- 6. Brain matter exposed or penetrating brain injury (GSW)
- 7. Isolated drowning or hanging victims
- 8. Isolated burns without evidence of traumatic injury
- 9. Referral Hospital In-patient admission
- 10. Objection to study voiced by subject or family member at scene
- 11. Wearing PPOWER opt-out bracelet

Inclusion and exclusion criteria will be assessed based on available information at the time of enrollment. Although all reasonable efforts will be made by the air medical crew to either directly witness or obtain documentation of eligibility criteria, due to the nature of the emergency pre-hospital setting, there may be occasions where the air medical crew must rely on verbal report of inclusion criteria, including qualifying vitals, from the referring hospital or ground crew. In these instances, if, after subsequent review of outside hospital and/or ground crew documentation, it is determined that the subject did not meet inclusion criteria and/or met exclusion criteria, the subject will remain enrolled in the study based on the intention-to-treat principle.

In the event that a verbal report must be used in lieu of physical documentation or directly witnessing the qualifying vitals, documentation of the verbal report will serve as the source documentation for determining eligibility. Verbal reports will be documented in the air medical record and will detail the information reported and by whom.

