If the PI and study team plan to modify the study, they will submit the amendment to the University of Pittsburgh HRPO along with all study documents to be changed (i.e. protocol, consent form, etc.) Once IRB approval is obtained, the study team will submit the changes to the NIH at the next reporting cycle unless earlier notification is warranted. If it is a significant change, the PI will request approval by the NIH Program Officer and DSMB prior to modification. Any changes will also be reviewed by the Office for Investigator-Sponsored IND and IDE Support (O3IS) for determination if the change requires prospective FDA review or if it can be submitted at annual report.

Data Analysis Plan Overall guideline:

- 1. Nature of this study: Pilot study
- 2. Overall objectives: Evaluate safety, efficacy, and feasibility of a LTLR-WB prehospital thru in-hospital protocol. The study will provide estimation for intra-cluster correlation coefficient and sample size variation across clusters for the design for a future full scope large clinical trail
- 3. Analysis Principle: Intent-to-treat for the prehospital randomization assignment. 95% confidence intervals for all measurements

Safety and Efficacy Analysis:

- 1. In-hospital mortality is the primary safety and efficacy outcome and will be compared across randomized groups.
- 2. LTLR-WB and Standard of Care arms will be compared using a pooled Z test of two independent proportions.
- 3. Survival analysis will be conducting looking at median survival at 3hr, 6hr, 24hr, and 28day time points across the two arms of the study testing the differences using log rank test.

Eligibility, Enrollment, and Subject Accrual:

The feasibility of enrollment will be evaluated by determining, ratio of the following parameters will be calculated along with 95% confidence intervals:

- 1) the number of patients that meet the eligibility criteria for the trial;
- 2) the proportion of eligible patients that can be randomized and

3) the proportion of eligible patients who are enrolled in the trial.

Additionally:

1. The reasons of not enrollment will be recorded with related frequency and percentages.

- 2. Frequency of patients eligible but not enrolled will be recorded
- 3. Frequency of patients randomized but not included in the study will be recorded
- 4. Rate of subjects' accrual per month with 95% C.I. will be calculated.

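### Section 6.4.7 lets an investigator who knows the arm withdraw patients found ineligible, and leaves their follow-up and analysis status undefined, against the intention-to-treat rule in 3.3

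*Combined protocol and SAP*

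**What the plan says.** Four places in the combined protocol and SAP bear on a patient found ineligible after enrolment.

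- **Section 6.4.7**, under its sub-heading on discontinuation of the trial: "The investigator may withdraw a subject from participating in this research if circumstances arise which warrant doing so". Two grounds follow. One is the subject's health and safety; the other is "because the subject's condition did not meet certain criteria needed for study inclusion".
- **Section 3.3**, after the exclusion list, explains that "there may be occasions where the air medical crew must rely on verbal report of inclusion criteria". If later review of the records shows that such a patient was not eligible, "the subject will remain enrolled in the study based on the intention-to-treat principle".
- **Section 2.9** sets the analysis population: "analyses will include all enrolled patients grouped by randomization assignment". The Data Analysis Plan in section 6.4.2 repeats intention to treat.
- **Section 6.4.2**, under eligibility and accrual: "Frequency of patients randomized but not included in the study will be recorded". Appendix 8, Table 3 has a matching row by arm. Neither place defines who falls into that group.

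On blinding, section 2.1 states: "The study is required to be open label due to the inability to blind blood or blood component transfusion". Under section 2.6, "an annual schedule of randomization assignment will be distributed to each study air base".

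**The concern.** Section 3.3 treats staying enrolled as the intention-to-treat safeguard. Section 6.4.7 gives a general discretion to withdraw on the very ground that section 3.3 says should not end enrolment. It sets no time limit and no independent or blinded review. It does not say whether withdrawal stops only research procedures, whether data already collected are kept, or whether vital status is still obtained.

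The analysis set is defined as enrolled patients, so the status of a withdrawn patient is open: still enrolled and counted, or no longer enrolled and left out. If some sites of judgement read it the second way, patients could leave the mortality comparison after allocation by a decision made with the arm known. Loss unrelated to arm and outcome costs power. Loss related to both biases the comparison, and with 56 patients per arm a few deaths can matter.

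**Working it through.** **Texts side by side.** For a patient enrolled on a verbal report and later found ineligible, section 3.3 requires continued enrolment and section 6.4.7 permits withdrawal; neither refers to the other. For a patient found ineligible in any other way, section 3.3's sentence does not apply, because it is confined to verbal-report cases. Only the discretion in 6.4.7 and the general statement in 2.9 then govern.

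**Inputs from section 2.9.** 56 per arm; mortality 33% v 11%; two-sided alpha 0.05; two looks at information 0.5 and 1.0 with boundaries 2.96259 and 1.96857; pooled Z test. The 33% is the plan's in-hospital control risk. The documents give no rate of late-found ineligibility, so every exclusion number below is an assumption.

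**Step 1: the plan's own power.** Pooled drift = 0.22 / √(0.22 × 0.78 × 2/56) = 2.8102. The two-look bivariate normal calculation gives alpha 0.0500, first-look power 0.1647 and total power 0.8010. The plan prints drift 2.81024 and power 0.800921, so its figure reproduces.

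**Step 2: non-selective loss.** Drift scales by √(n/56). If about 5%, 10% or 20% are lost (53, 50 or 45 per arm), power is 77.9%, 75.5% or 71.0%.

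**Step 3: selective loss, no true effect.** Deaths x (whole blood) and y (standard care) are independent Binomial(56, 0.33). Remove k' = min(k, x) whole-blood deaths, compute

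z = [(x−k')/(56−k') − y/56] / √{p(1−p)[1/(56−k') + 1/56]}, with p = (x−k'+y)/(112−k'),

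and add the exact probabilities where z lies beyond ±1.96857. This treats the final test alone, without the interim look or clustering.

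| Whole-blood deaths removed | Favours whole blood | Favours standard care | Two-sided |
|---|---|---|---|
| 0 | 2.6% | 2.6% | 5.2% |
| 1 | 3.4% | 1.8% | 5.3% |
| 2 | 5.1% | 1.4% | 6.5% |
| 3 | 6.8% | 1.0% | 7.8% |
| 4 | 9.6% | 0.7% | 10.2% |

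**Step 4: one worked data set.** Suppose 10/56 whole-blood and 18/56 standard-care deaths.

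- None removed: p = 28/112 = 0.25; z = −0.1429 / √(0.25 × 0.75 × 2/56) = −1.75, inside the boundary.
- One whole-blood death removed (9/55): z = −1.94, still inside.
- Two removed (8/54): p = 26/110 = 0.2364; z = −0.1733 / 0.0810 = −2.14, beyond 1.96857.

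**The case against.** The best defence is that withdrawing from participation is not the same as leaving the analysis. Section 6.4.7 never mentions the analysis set, and sections 2.9 and 6.4.2 commit to intention to treat. Section 5.1 applies the same principle to patients first identified after arrival in the emergency department. Other sections help as well: 6.5.1 requires a case report form for every enrolled subject and keeps data indefinitely; 2.8 allows 28-day vital status from chart review or the social security death index; and Appendix 4 recognises that making chart review depend on consent could bias the results. The row for patients randomized but not included sits among feasibility measures, so it is not evidence of planned exclusion from the mortality comparison.

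Most of this stands, and it limits what can be claimed. A reader might infer any of the following, none of which the documents support:

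- **That 6.4.7 removes ineligible patients from the analysis.** It is silent on this, and 2.9 points the other way.
- **That the two rules cannot both be followed.** Section 6.4.7 is permissive and 3.3 mandatory, so an investigator can obey both by not using the discretion in verbal-report cases.
- **That eligibility often rests on verbal report.** Section 3.3 speaks of possible occasions after reasonable efforts to witness or document eligibility.
- **That the investigator also knows the outcome when withdrawing a patient.** The text supports knowledge of the arm; it says nothing about timing relative to death.

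The defence does not close the gap. None of the helpful provisions mentions investigator withdrawal. Section 6.4.2 describes follow-up of withdrawn participants only for the resolution of serious adverse events. And the set in 2.9 depends on the word enrolled, which is the status that 6.4.7 puts in doubt.

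**Conclusion.** The point holds as an inconsistency to be corrected. It is not a demonstrated bias. The plan contains a stated discretion that works against its own intention-to-treat safeguard, and it leaves the follow-up and analysis status of patients withdrawn under it undefined. The tension is direct for verbal-report cases; for other late-found ineligible patients there is no specific rule.

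The size cannot be estimated, because the documents give no frequency. The figures are illustrations. Steps 3 and 4 assume that only deaths, and only from the whole-blood arm, are removed every time. Removing two then takes the error favouring whole blood from about 2.6% to 5.1%, but the two-sided rate only from about 5.2% to 6.5%, since the opposite tail shrinks. The data set in step 4 was chosen close to the boundary, and one removal does not cross it. What the figures do show is that in a trial of 112 patients a handful of discretionary losses could alter the primary result. That is reason enough to change the wording.

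**What to change.** 1. In section 6.4.7, delete failure to meet inclusion criteria as a ground for withdrawal, or limit it to stopping further research procedures. The health-and-safety ground is not affected.
2. In sections 3.3 and 2.9, state for all patients later found ineligible, however eligibility was first established, that they keep their assigned arm, have 28-day vital status ascertained where consent rules allow, and stay in the primary intention-to-treat analysis.
3. Report the number of such patients by arm. Define the line for patients randomized but not included (section 6.4.2 and Appendix 8, Table 3) consistently with this.

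The cost is a sentence or two of protocol text and one table definition. Sample size stays at 56 per arm and power at 80.1%. Vital status can come from sources already named in section 2.8.
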